## **9.0 Efficacy Analyses**

### **9.1 General Considerations**

All primary and secondary endpoints will be analyzed in the ITT 1 Population to test the superiority of upadacitinib over dupilumab in Period 1. All tests will be 2-sided at an alpha level of 0.05.

All efficacy endpoints will be summarized descriptively using ITT 2 Population in Period 2. Subjects will be included in the treatment group to which they are randomized.

In Period 1, categorical endpoints will be analyzed using Cochran-Mantel-Haenszel (CMH) test stratified by vIGA-AD categories (vIGA-AD 3; 4) and age (12 to < 18; 18 to < 40; ≥ 40 to < 64 years). For categorical endpoints, missing values and visits after the rescue will be handled by non-responder imputation (NRI) except for missing values due to COVID-19 or any other missing data that can be reasonably assumed to be Missing at Random, which will be handled by multiple imputation (NRI-MI).

In Period 2, categorical endpoints will be summarized by counts and percentages, as well as 95% confidence interval (CI) of the percentage. The primary approach to handle missing data is Observed Cases (OC), which is defined in Section 9.2.

### **Analysis of Categorical Variables**

Models of Categorical Variables in Period 1 and Period 2 are summarized in [Table 2](#).

**Table 2. Model of Categorical Variables in Period 1 and Period 2**

Period	Type of Variables	ITT Populations	Imputation Method	Intercurrent Events Handling	Analysis Model
Period 1	Categorical	ITT 1	NRI-MI	Subjects will be considered as non-responders after the initiation of rescue medication (composite variable strategy); and the value for the variable of interest is used regardless of treatment discontinuation (treatment policy strategy)	CMH test stratified by vIGA-AD categories (3; 4) and age (12 to < 18; 18 to < 40; ≥ 40 to < 64 years)
Period 2	Categorical	ITT 2	OC		Summarized by counts and percentages (with 95% confidence interval)

Unless otherwise specified, any subject randomized into an incorrect stratum will be analyzed according to the actual stratum the subject belongs to. During derivation, any subject not already within the current strata will be included in the nearest stratum.

## **9.2 Handling of Missing Data**

In Period 1, missing values and visits after the rescue will be handled by non-responder imputation (NRI) except for missing values due to COVID-19 or any other missing data that can be reasonably assumed to be Missing at Random, which will be handled by multiple imputation (NRI-MI).

- The NRI-MI will categorize any subject who does not have an evaluation during a pre-specified visit window (either due to missing assessment or due to early withdrawal from the study) as a non-responder for the visit. The only exceptions are: 1) when the subject is a responder both before and after the visit window, the subject will be categorized as a responder for the visit. 2) missing data due to COVID-19 infection or logistical restriction or any other missing data that can be reasonably assumed to be Missing at Random, will be handled by Multiple Imputation. In addition, all assessments after the start of rescue medications will not be included in the analyses; as a result, subjects will be counted as non-responders thereafter and will not be imputed by MI. Random seeds are provided in [Appendix D](#). NRI-MI is the primary approach to handle missing data for categorical endpoints in Period 1.
- Non-responder Imputation (NRI): NRI will be performed in the same way as NRI-MI without the exception #2 above. That is, missing due to COVID-19 infection or logistical restriction or any other missing data that can be reasonably assumed to be Missing at Random, will also be counted as non-responders. The NRI is a missing data handling method in a sensitivity analysis for the primary endpoint.

Subjects whose change/percent change from Baseline cannot be calculated because of a missing Baseline will be considered as a non-responder at all post-baseline visits in both NRI-MI and NRI approaches.

Multiple Imputation (MI): another missing data handling method performed in a sensitivity analysis for the primary endpoint. Markov Chain Monte Carlo (MCMC) will be first applied to augment data into monotonic missing pattern and PROC MI will be used to generate 30 datasets using the regression method.

- The imputation is done in two steps for the primary endpoint.
- Step 1: The EASI 90 and WP-NRS 0/1 (based on weekly average) are imputed separately.

For example, for EASI 90, the variables to be included in the imputation model are treatment group, major stratum (vIGA-AD categories and age),

Baseline, and measurements at each visit in Period 1. The random seed for MCMC and the random seed for PROC MI are specified in [Appendix D](#). The imputed post-baseline measurements will be rounded to the same precision as the observed data before the determination of responder status. WP-NRS 0/1 will be imputed by the same imputation model as EASI 90.

- Step 2: After obtained the EASI 90 and WP-NRS 0/1 (based on weekly average) at Week 16 based on MI imputed values separately, subjects will be characterized as responders or non-responders based on MI imputed datasets. Using the Cochran-Mantel-Haenszel (CMH) model adjusted by main stratification factors (vIGA-AD categories and age), the imputed endpoints will be analyzed using each of the 30 datasets. SAS PROC MIANALYZE will be used to generate the final inferences of the risk difference between upadacitinib and dupilumab. Note that measurements will be considered as missing after the first dose of rescue treatment before MI. Regardless of MI imputed values, subjects after receiving rescue medications will be counted as non-responders.

In Period 2, the primary approach to handle missing data is Observed Cases (OC).

- The OC analysis will not impute values for missing evaluations, and thus a subject who does not have an evaluation at a scheduled visit will not be included in the OC analysis for that visit. The OC analysis will be performed for all variables and will not include values after more than 1 day after discontinuation of study drug.

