## **2.4 Sample Size Determination**

Approximately 880 subjects will be randomized to upadacitinib or dupilumab in a 1:1 ratio. Assuming a response rate of 12% in achieving both EASI 90 and WP-NRS 0/1 at Week 16 in the dupilumab arm, this sample size will provide more than 90% power to detect the treatment difference of 17% (upadacitinib versus dupilumab), using a two-sided significant level of 0.05. Sample size calculations were performed using nQuery Version 9.1.1.0.

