### A. Random Seeds for NRI-MI

Endpoints	Random Seed	
	MCMC procedure	PROC MI
EASI 90 and WP-NRS 0/1 at Week 16 a	1001 for EASI 90; 1002 for WP-NRS	9001 for EASI 90; 9002 for WP-NRS
EASI 90 at Week 16	1003	9003
WP-NRS 0/1 at Week 16 among subjects with Baseline WP-NRS > 1	1004	9004
An improvement (reduction) in WP-NRS $\geq 4$ at Week 16 among subjects with Baseline WP-NRS $\geq 4$ b	1005	9005
WP-NRS 0/1 at Week 4 among subjects with Baseline WP-NRS > 1 c	1006	9006
WP-NRS 0/1 at Week 2 among subjects with Baseline WP-NRS > 1 d	1007	9007
EASI 90 at Week 4 e	1008	9008
EASI 75 at Week 2 a	1009	9009
EASI 100 at Week 16 a	1010	9010
Achievement of 75% reduction in EASI in the head and neck region from Baseline at Week 2, 4, 8, 12, 16	1011	9011
Achievement of 75% reduction in EASI in the trunk region from Baseline at Week 2, 4, 8, 12, 16	1012	9012

Endpoints	Random Seed	
	MCMC procedure	PROC MI
Achievement of 75% reduction in EASI in the upper extremities region from Baseline at Week 2, 4, 8, 12, 16	1013	9013
Achievement of 75% reduction in EASI in the lower extremities region from Baseline at Week 2, 4, 8, 12, 16	1014	9014

Notes:

- The random seed for the corresponding endpoint at the other visits (i.e., Week 2, 4, 8, 12) will use the random seed for that endpoint at Week 16, except EASI 75 where the random seed for this endpoint at the other visits (i.e., Week 4, 8, 12, 16) will use the one at Week 2.
- The random seed for an improvement (reduction) in WP NRS  $\geq 4$  at the other visits (i.e., Week 1, 2, 3, 4, 5, 6, 7, 8, 9, 10, 11, 12, 13, 14 and 15) will use the random seed for this endpoint at Week 16.
- The random seed for WP NRS 0/1 at Week 5, 6, 7, 8, 9, 10, 11, 12, 13, 14 and 15 will use the random seed for this endpoint at Week 4.
- The random seed for WP NRS 0/1 at Week 1 and 3 will use the random seed for this endpoint at Week 2.
- The random seed for EASI 90 at the other visits (i.e., Week 2, 8 and 12) will use the random seed for this endpoint at Week 4.

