#### **Augmentation Step**

For datasets with non-monotone missing data pattern, the augmentation step will first impute enough values to augment the data into a monotonic missing pattern:

Markov Chain Monte Carlo (MCMC) will be applied to augment the data using PROC MI with the MCMC IMPUTE monotone statement, assuming a multivariate normal distribution. The augmented data will be used in the subsequent imputation step to generate 'complete' datasets. Covariates included in the model are treatment, stratification factors (vIGA-AD categories (vIGA-AD 3; 4) and age (12 to < 18; 18 to < 40;  $\geq 40$  to < 64 years)), Baseline, and all post-baseline visits of the outcome variable according to the pre-specified order. Of note, categorical variables are included using the form of dummy variables.

Repeat the imputation process K 30 times using the procedure described above to form K 30 monotone missing datasets, where K is determined as described in "Repetition of Imputations (K)."

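### EASI and WP-NRS are imputed in separate models before the composite is formed, so their residual correlation is dropped where Week 16 data are imputed; the effect is small, and a joint model is a cheap improvement

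*SAP*

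**What the plan says.** SAP Section 9.2 describes full MI, a sensitivity analysis for the primary endpoint, in two steps. In Step 1, "The EASI 90 and WP-NRS 0/1 (based on weekly average) are imputed separately". The EASI model holds treatment, the vIGA-AD and age strata, Baseline and the Period 1 measurements. WP-NRS gets a model of the same form. Step 2 derives responder status from the two sets of imputed values and runs the CMH analysis on each of 30 datasets.

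The primary method, NRI-MI, follows the same pattern. SAP Appendix D, Table A gives the composite two MCMC seeds, "1001 for EASI 90; 1002 for WP-NRS", and two PROC MI seeds. In Appendix H Section 2.3 the covariates are treatment, the strata and "Baseline, and all post-baseline visits of the outcome variable according to the pre-specified order". The sample code in Appendix H Section 3.0 lists EASI visits only. Neither component appears in the other's model.

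In NRI-MI, only data missing because of COVID-19, or otherwise judged missing at random, are multiply imputed. Other missing data and all visits after rescue count as non-response (SAP Section 9.2; Appendix H Section 2.4).

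**The concern.** The composite is a joint event. Two components drawn independently, each given only its own history, are conditionally uncorrelated at the imputed visit. If skin clearance and itch relief tend to occur together beyond what those histories explain, too few subjects are imputed as meeting both criteria.

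The case with one component missing is realistic here. WP-NRS is scored daily on a handheld device, whereas EASI needs a blinded assessor at a visit (Protocol Appendix D; SAP Section 9.7). A visit missed through quarantine or travel limits, which is the situation Appendix H Section 1.1 has in mind, can leave Week 16 itch recorded and EASI missing. The EASI model then makes no use of that itch score, although using related observed data would make the missing-at-random assumption more credible.

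At stake are the composite response rates in the imputed subset and, through them, the estimated treatment difference.

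**Working it through.** **1. The plan's own figure.** SAP Section 2.4 plans for about 880 subjects split equally between the arms, a 12% composite rate on dupilumab, a 17-point difference and two-sided alpha 0.05. It claims that "this sample size will provide more than 90% power". So n = 440 per arm, 12% v 29%, pooled rate 20.5%.
- SE under the null = √(2 × 0.205 × 0.795 / 440) = 0.0272
- SE under the alternative = √((0.12 × 0.88 + 0.29 × 0.71) / 440) = 0.0266
- z = (0.17 − 1.96 × 0.0272) / 0.0266 = 4.38, so power is 99.999%. The claim of more than 90% is true.

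**2. Assumed inputs.** The documents give no component response rates, no EASI/WP-NRS correlation and no expected share of imputed data. I assume EASI 90 / WP-NRS 0/1 rates of 45%/40% (upadacitinib) and 25%/25% (dupilumab), normal latent scales, and cross-correlation ρ from 0.3 to 0.7. The autocorrelation between Weeks 12 and 16 is 0.75, and the correlation of one scale at Week 16 with the other at Week 12 is 0.75ρ.

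**3. Formulae.** Let Φ₂(a, b; r) be the bivariate-normal probability of meeting both criteria.
- Correct rate: Φ₂ at r = ρ.
- Separate models, each using its own Week 12 value: the imputed pair has correlation 0.75 × 0.75 × ρ = 0.5625ρ, so the rate is Φ₂ at r = 0.5625ρ.
- Separate models, no post-baseline history: the product of the two component rates, 18.0% (0.45 × 0.40) and 6.25% (0.25 × 0.25).
- Only one component missing, with history: observed Week 16 EASI against imputed WP-NRS has correlation 0.75 × 0.75ρ = 0.5625ρ, so the shortfall is the same.

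**4. Results among imputed subjects (%; shortfall in points).**

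| ρ | Upa correct | Upa with history | Upa none | Dupi correct | Dupi with history | Dupi none |
|---|---|---|---|---|---|---|
| 0.3 | 22.7 | 20.6 (−2.1) | 18.0 (−4.7) | 9.5 | 8.0 (−1.5) | 6.25 (−3.3) |
| 0.5 | 26.0 | 22.4 (−3.7) | 18.0 (−8.0) | 12.0 | 9.3 (−2.7) | 6.25 (−5.8) |
| 0.7 | 29.9 | 24.2 (−5.7) | 18.0 (−11.9) | 15.0 | 10.6 (−4.4) | 6.25 (−8.8) |

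**5. Effect on the treatment difference.** Among imputed subjects the loss is the upadacitinib shortfall minus the dupilumab shortfall: 0.6 to 1.3 points with history (5.7 − 4.4 = 1.3 at ρ = 0.7) and 1.4 to 3.1 without (11.9 − 8.8 = 3.1). If 10% of each arm is imputed, multiply by 0.10: 0.06 to 0.13 points with history and 0.14 to 0.31 without.

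**6. Unequal shares.** At ρ = 0.5 with history, 10% imputed on dupilumab and 2% on upadacitinib gives 0.10 × 2.7 − 0.02 × 3.7 = +0.20 points, in favour of upadacitinib. Swapping the shares gives 0.02 × 2.7 − 0.10 × 3.7 = −0.32 points.

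**7. Check anchored to the plan's 12% and 29%.** Take equal component rates within each arm, solved to give those composites. At correlation 0.6 they are 23.0% and 43.6%. With no history the imputed rates are 5.3% and 19.0%, shortfalls of 6.7 and 10.0 points, so at 10% imputed the difference falls by 0.10 × (10.0 − 6.7) = 0.33 points. Over correlations 0.4 to 0.8, simulating visits at Weeks 2 to 16 as well, the loss at 10% imputed is 0.05 to 0.55 points. Even at 30% imputed and correlation 0.8 with no history, the difference is 15.4 points and power stays above 99.9%.

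**The case against.** The strongest reply is that nothing in the trial's conclusion depends on this. Multiple imputation in the primary analysis covers only COVID-19 or otherwise missing-at-random data, and early withdrawal defaults to non-response, so the imputed share may be well below 10%. The pre-specified NRI sensitivity analysis counts these subjects as non-responders. With 10% imputed in each arm, that alone removes 0.10 × 17 = 1.7 points from the planned difference, more than separate imputation does. Appendix D also lists WP-NRS endpoints for every week to Week 15; if those averages entered the model, the history would be closer than Week 12 and the shortfall smaller. All of this stands and limits the point to a refinement. It does not justify the separate models, because no planned analysis shows the result under joint imputation.

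A reader might also infer four stronger things that the documents do not support:
- *The correlation is lost.* Treatment, strata and own history carry part of it. In the step 4 scenarios, Week 12 history removes about half of the shortfall.
- *An observed component is ignored.* It is absent from the other scale's model, but Step 2 still uses it. An observed non-response on either scale settles the composite as non-response.
- *The difference is always biased towards zero.* That needs positive residual correlation and similar imputed shares by arm.
- *The differing seeds create bias.* Ranked endpoints 1 and 2 re-impute the same scales with seeds 1003 and 1004. Within one numbered imputation a subject can therefore meet the composite and fail EASI 90. This is Monte Carlo incoherence; each endpoint is tested on its own pooled estimate.

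**Conclusion.** The point holds as a modest modelling weakness in both the primary NRI-MI and the MI sensitivity analysis. The composite is formed from two imputation models, neither of which contains the other component. With positive residual correlation, the composite rate among imputed subjects is too low by about 1.5 to 6 points with Week 12 history and 3 to 12 points without. At 10% imputed in each arm the treatment difference shrinks by about 0.06 to 0.3 points, against a planned 17. With unequal shares the direction can reverse, so the method should not be described as conservative. Power is not threatened.

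The sizes rest on assumptions from outside the documents: the component rates, the correlations, normal latent scales and the imputed share. The assumed rates imply composite differences of 13.2 to 14.9 points (22.7 − 9.5 to 29.9 − 15.0) rather than exactly 17. The check anchored to 12% and 29% gives losses of the same order.

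**What to change.** Replace the separate models with one. Impute EASI and the WP-NRS weekly average (Baseline and Weeks 2, 4, 8, 12 and 16) together in a single MCMC and monotone-regression model with treatment and strata. Keep any further weekly WP-NRS averages that are available, so that diary information is not discarded. Derive the composite and all ranked endpoints from the same 30 completed datasets, in both NRI-MI and MI, applying the non-responder and rescue rules afterwards as now. This also removes the incoherence between the composite and the single-component endpoints.

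The cost is revised wording in SAP Section 9.2 and Appendix H, a shorter seed table and a longer variable list. The drawback is a larger model with two bounded, rounded scales, so convergence must be checked; Appendix D already has a rule for non-convergence. If separate models are kept, the SAP should say why they suffice.

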## **9.3 Primary Efficacy Endpoint and Analyses**

### **9.3.1 Primary Efficacy Endpoint**

The primary endpoint is the achievement of both EASI 90 and WP-NRS 0/1 at Week 16.

### **9.3.2 Main Analysis of Primary Efficacy Endpoint**

For the primary endpoint, comparisons between upadacitinib and dupilumab will be conducted using the CMH test on ITT 1 Population, adjusting for vIGA-AD categories

(vIGA-AD 3; 4) and age (12 to < 18; 18 to < 40;  $\geq$  40 to < 64 years). NRI-MI will be the primary approach to handle missing values.

In Period 1, frequencies and percentages will be provided along with 95% CIs. Point estimates, 95% CIs and p-values from the CMH test for the difference in proportions between upadacitinib and dupilumab will be provided.

The attributes of the estimand corresponding to the primary efficacy objective are summarized in [Table 3](#).

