#### **Baseline Characteristics**

- Baseline EASI (< median,  $\geq$  median)
- Body Surface Area (BSA) in percentage
- Baseline vIGA-AD (3, 4)
- Previous systemic therapy (with and without)
- EASI overall score and body region scores

- Worst Pruritus NRS (Weekly Average)
- Prior Atopic Dermatitis Treatment
- Disease duration since diagnosis (years)
- Disease duration since symptoms started (years)
- Duration between symptoms and diagnosis (years)

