### **9.4.2 Main Analyses of Key Secondary Efficacy Endpoint(s)**

In Period 1, the ranked secondary efficacy endpoints will be analyzed by comparing upadacitinib and dupilumab. The categorical endpoints will be analyzed by CMH test on ITT 1 Population, adjusting for vIGA-AD categories (vIGA-AD 3; 4) and age (12 to < 18; 18 to < 40;  $\geq 40$  to < 64 years).

The attributes of the estimands corresponding to the key secondary efficacy objectives are summarized in [Table 4](#).

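### The Period 1 CMH analyses are valid but leave baseline EASI and baseline WP-NRS unused; the possible cost is a small loss of precision, chiefly for the ranked itch endpoints

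*SAP*

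**What the plan says.** For the primary endpoint, SAP 9.3.2 says that "comparisons between upadacitinib and dupilumab will be conducted using the CMH test on ITT 1 Population, adjusting for vIGA-AD categories" and age group. For the ranked secondary endpoints, SAP 9.4.2 says: "The categorical endpoints will be analyzed by CMH test on ITT 1 Population, adjusting for vIGA-AD categories", again with age group. SAP 9.1, Table 2 and 9.5 repeat the two factors, and Protocol 7.4 names the same stratified CMH test. The sample code in SAP Appendix H 3.0 computes a Mantel-Haenszel risk difference stratified by age group and vIGA-AD group only.

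Baseline EASI and baseline WP-NRS appear elsewhere:

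- Protocol 5.1 makes both entry criteria: EASI of at least 16, and a weekly WP-NRS average of at least 4 based on at least 4 of 7 daily scores.
- SAP 7.1 lists EASI and "Worst Pruritus NRS (Weekly Average" among the baseline characteristics.
- In the augmentation step of Appendix H 2.3, the model contains treatment, the stratification factors, "Baseline, and all post-baseline visits of the outcome variable according to the pre-specified order". SAP 9.2 gives WP-NRS the same model form as EASI.
- SAP 9.6 uses baseline EASI to form subgroups for the primary endpoint.

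No Period 1 test or interval adjusts for either score.

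**The concern.** The strata are two-level vIGA-AD and three-level age. vIGA-AD is a coarse measure of skin severity, and neither factor carries baseline itch. Yet five of the nine ordered hypotheses depend on itch: the primary and ranks 2 to 5. Four of these (the primary and ranks 2, 4 and 5) use the absolute threshold WP-NRS 0/1. Reaching 0 or 1 from a baseline of 4 is a different task from reaching it from 9, so baseline itch could plausibly predict response.

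What is at stake is precision. SAP 13.0 tests the endpoints in strict order at 0.05, and one non-significant result ends formal testing. The documents give no assumed rates or power for any ranked secondary endpoint, so there is no stated margin against such a miss. If the baselines are prognostic, adjusting for them gains precision without extra subjects. A standardised risk difference is still the marginal difference in proportions defined in SAP Tables 3 and 4, so the estimand does not change.

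**Working it through.** **1. The plan's own figure.** Inputs from SAP 2.4: "Approximately 880 subjects will be randomized to upadacitinib or dupilumab in a 1:1 ratio" (440 per arm); a control rate assumed at 12%, as the plan puts it for dupilumab; "this sample size will provide more than 90% power to detect the treatment difference of 17" percentage points, so 29% against 12%; "using a two-sided significant level of 0.05".

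- SE under the null, pooled rate 0.205: √(2 × 0.205 × 0.795 / 440) = 0.0272.
- SE under the alternative: √[(0.12 × 0.88 + 0.29 × 0.71) / 440] = 0.0266.
- z = (0.17 − 1.96 × 0.0272) / 0.0266 ≈ 4.38, so power is above 99.99%.

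The stated lower bound of 90% is met. Only 117 per arm would be needed for 90% power (128 with continuity correction). At 440 per arm, 90% power is reached for a difference of about 8 points.

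**2. Planned interval (unadjusted approximation).** Half-width = 1.96 × 0.0266 = 5.22 points, so a 17-point difference has an interval of about 11.8 to 22.2.

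**3. Effect of adjustment by formula.** Let R² be the share of outcome variance that the two baselines explain beyond the strata. The documents give no value, so a range is assumed. Half-width becomes 5.22 × √(1 − R²); the equivalent extra sample is 880/(1 − R²) − 880.

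| Assumed R² | Half-width (points) | Narrower by | Equivalent extra subjects |
|---|---|---|---|
| 1% | 5.19 | 0.5% | 9 |
| 2% | 5.16 | 1.0% | 18 |
| 5% | 5.08 | 2.5% | 46 |
| 10% | 4.95 | 5.1% | 98 |
| 20% | 4.66 | 10.6% | 220 |

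**4. Effect of adjustment by simulation.** Each simulation had 880 subjects, six strata and 1,500 to 3,000 trials per scenario. It compared a logistic model standardised to a marginal risk difference with the stratified Mantel-Haenszel (MH) risk difference. The assumed quantity is the SD of the added prognostic score on the log-odds scale. Narrowing = 1 − √(variance ratio); for example, 1 − √0.862 = 7.2%.

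| Rates | SD 0.4 | SD 0.7 | SD 1.0 |
|---|---|---|---|
| 12% vs 29%: variance ratios, three simulations | 0.970, 0.975, 0.97 | 0.923, 0.927, 0.94 | 0.862, 0.885, 0.85 |
| 12% vs 29%: narrowing | 1.5, 1.3, 1.5% | 3.9, 3.7, 3.0% | 7.2, 5.9, 7.8% |
| 5% vs 12% (assumed): narrowing | 1.1% | 1.7% | 4.7% |
| 5% vs 10% (assumed): narrowing | 0.5% | 2.0% | 3.0% |
| 3% vs 8% (assumed): narrowing | 0.3% | 1.6% | 2.5% |
| 3% vs 7% (assumed): narrowing | 0% | 1.0% | 2.0% |

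At 12% vs 29%, SDs of 0 and 0.2 gave ratios of 1.003 and 1.005, which is no gain. A further simulation over SD 0 to 1.0 gave narrowing of 0 to 5% at 12% vs 29% and 0 to 2% at 3% vs 8%. Monte Carlo error is about 1 to 2%.

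Another simulation modelled the two baselines separately, with a correlation of 0.3. Narrowing was about 0% at an odds ratio per SD of 0.82 for each score, 1.9% at 0.74, 4.0% at 0.61 and 9.6% at 0.45. The last case implies a combined SD of 0.8 × √2.6 ≈ 1.29, outside the range above. Mean adjusted and MH estimates agreed within 0.001 in the comparisons made.

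**5. Power for modest differences.** Replacing 440 by 440/(1 − R²) in the formula of step 1:

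| Assumed rates | No adjustment | R² 5% | R² 10% |
|---|---|---|---|
| 12% vs 18% | 70.3% | 72.5% | 74.8% |
| 12% vs 20% | 90.0% | 91.4% | 92.8% |

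**The case against.** The strongest reply is that nothing here is wrong. CMH stratified by exactly the randomisation factors matches the design and gives the planned difference in proportions. That stands, and the point is one of efficiency only.

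Three stronger readings are tempting, and the documents do not support them.

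- *Adjustment would narrow every interval.* The gain depends on prediction beyond the strata, which the documents do not quantify. There are reasons to expect it to be limited: EASI 90 is already scaled to baseline EASI, vIGA-AD carries part of the severity information, entry thresholds truncate both scores, and ranks 1, 6, 7 and 8 contain no itch component.
- *The early endpoints gain most because responders are few.* The simulations point the other way: relative gains shrink as responses become rarer. Subject equivalents at 12% vs 29% cannot be carried over to Weeks 2 and 4, whose expected rates are not in the documents.
- *The imputation and analysis models are inconsistent.* Each imputation model holds only the baseline of its own score and affects only imputed values. Omitting that score from the comparison is no contradiction.

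Two practical objections also stand. Protocol 7.4 itself names CMH, so the change is a departure from the protocol. The SAP is already at version 4.0 in a trial where only the efficacy assessor is blinded, so a late change to the primary estimator would need clear documentation. Also, both baselines are required at entry, but SAP 9.2 still foresees missing ones, and a covariate model without a rule would drop those subjects from ITT 1.

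These points limit the size of the gain and add conditions to the fix. They do not remove the possible gain: adjustment cost no meaningful precision in any scenario run.

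**Conclusion.** The point holds as a minor, optional improvement. The planned CMH analyses are valid but leave two available baseline scores unused, and the strata contain no itch information. For an assumed prognostic SD of 0 to 1.0 beyond the strata, intervals are about 0 to 7% wider than necessary at 12% vs 29%; the separate simulations put the upper end between 5% and just under 8%. At an assumed 3% vs 8% the excess is about 0 to 2.5%. The prognostic strength and all rates other than 12% and 29% are assumptions.

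The primary conclusion is not affected. At best, a ranked endpoint with a modest difference gains a few points of power, and the case is strongest for the itch endpoints. No ranked endpoint has been shown to be at risk.

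**What to change.** Before the Period 1 lock, pre-specify the following in SAP 9.3.2, 9.4.2 and Appendix H 2.5:

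- **Estimator.** A risk difference standardised (g-computation) from a logistic model with treatment, vIGA-AD, age group, baseline EASI and baseline WP-NRS, with a robust SE. Combine it over imputations by Rubin's formula as planned. Appendix H 2.5.2 already bases inference on a risk difference and its SE, so the substitution is like for like. A conditional odds ratio should not replace it, because that would change the estimand.
- **Missing baseline.** A rule that keeps every subject in ITT 1, such as a simple fill-in of the covariate. The outcome stays as the SAP plans: non-response where change from baseline cannot be calculated.
- **Non-convergence.** A fixed fallback to stratified CMH, with its trigger defined in advance, since sparse endpoints are the likeliest to need it.
- **Sensitivity analysis.** Keep stratified CMH as planned.
- **Record.** Enter the departure from Protocol 7.4 in SAP 14.1.

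The cost is SAP wording, programming, a slightly more complex analysis and a documented departure from the protocol's CMH wording. If the sponsor prefers to leave the primary test as CMH, using the adjusted estimator for the ranked secondary endpoints only would keep most of the benefit. A pre-specified supplementary analysis would give the narrower intervals but would not help the hierarchy.
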